#### **5.4.Data source and collection**

Data was collected at baseline, Eighteen months, and end of the study (Thirty-six months). Structured questionnaires were used to collect information about patient-reported outcomes. In addition, the pharmacy information network (PIN) is an objective dataset that will be used to assess medication adherence.

#### **5.5.Randomization**

Using a scheme developed within REDCap by the University of Calgary's clinical research unit, randomization was completed using random small (<8) variable permuted blocks. This method will ensure robust allocation concealment. Randomization was stratified based on age (</≥70 years), gender (man/woman), and low household income status (defined by household-size specific Low-Income Cut-offs).

#### **5.6.Sample size**

The calculated sample size was 4714, considering the annual 1% migration from Alberta for three years. We estimated the sample size required for Poisson regression analysis and assumed no interaction between our two interventions. The assumption of no interaction was verified by running simulations using 25% and 50% interactions that had negligible effect on the power.

### **6. Statistical principles**

#### **6.1.Confidence interval and P-values**

We will calculate all analyses' 95% confidence interval and P-values using the appropriate statistical tests. We will consider findings as significant for P-values of 0.05 or lower.

### **7. Analysis Methods**

#### **7.1.Participant characteristics**

We will conduct descriptive analyses to characterize the distribution of the study participants. We will use the mean, median, standard deviation, and interquartile range after the normality test for distribution (histogram and quantile-quantile (QQ) plots). We will also determine the baseline mean scores of the four outcomes in each intervention group.

#### **7.2.Handling missing data**

To deal with missing data, we will thoroughly evaluate the dataset to understand the extent and pattern of missingness. We will classify the pattern as either missing at random (MAR) or missing not at random (MNAR).

We will employ multiple imputations or other suitable techniques deemed appropriate for MAR (19). If the pattern is MNAR, then we will test different scenarios of assumptions using sensitivity analyses and report with the limitations.

Finally, to ensure the validity and reliability of our findings, we will conduct sensitivity analyses. The approaches we selected to deal with and the pattern of missing data will be reported in the final manuscript.

### 7.3. Covariates

Considering randomization was successful, only Age, Sex, and Income status will be used for adjustment because these were the variables upon which the randomization was stratified. The literature also recommends this practice to improve discriminatory power.

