**5.3. Outcomes**

**a. Beliefs About Medication Questionnaire (BMQ).**

The mean score for BMQ will be calculated for each individual. Then, we will categorize it as 12 or below and over 12. We will also individually calculate the needs and concerns of subscales to localize further where issues arise.

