### 7.5. Outcome analysis

#### Tests for Objective #1:

We will conduct log-binomial regression to estimate the effect of the two interventions on belief about medication and medication self-efficacy and needs concern. Similarly, medication adherence will be analyzed using Robust Poisson Regression.

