7.2. Baseline Characteristics

Baseline characteristics will be reported in a Table using descriptive summary statistics. These will be stratified by group assignment, and t-tests/Chi2 tests will be used to examine for inter-group differences in these characteristics.

8. Data Sources

The main data source for the trial will be the ACCESS trial RedCAP database. This contains participant group assignments and all patient reported measures from baseline, 6-month, 18-month, and 33-month surveys. It also contains individuals' unique provincial health number which will permit deterministic linkage to administrative health databases held by Alberta Health (including Alberta Precision Laboratory data, Pharmacy Information Network Data, Practitioner Claims data, Discharge Abstract Database, National Ambulatory Care Reporting System data). All PHNs were verified at the time of study enrollment to be sure that they were accurate and active. In cases where a deterministic linkage is not possible, probabilistic linkage using name, date of birth, and postal code will be used.

9. Interventions (s)

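### SAP 7.3 leaves the baseline value of the same score out of the BMQ and MASES models; adding it as a categorical term is a cheap gain in precision

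*SAP*

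**What the plan says.** SAP 7.3 (Covariates) assumes that randomisation succeeded and states that "only Age, Sex, and Income status will be used for adjustment because these were the variables upon which the randomization was stratified". It adds a second reason: "The literature also recommends this practice to improve discriminatory power".

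SAP 7.5, under Objective 1, gives the model: "We will conduct log-binomial regression to estimate the effect of the two interventions on belief about medication and medication self-efficacy and needs concern". It lists no baseline term. Medication adherence is assigned to robust Poisson regression in the same paragraph.

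SAP 5.3 cuts the overall BMQ score at 12 and makes MASES binary. For the BMQ subscales it says only that "We will also individually calculate the needs and concerns of subscales to localize further where issues arise". That they will be analysed as binary variables is inferred from 7.5, since 5.3 gives them no cut-off.

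On baseline data, SAP 5.4 lists baseline among the collection times, and SAP 7.1 says "We will also determine the baseline mean scores of the four outcomes in each intervention group". The combined protocol and SAP (the parent plan), section 8 (Data Sources), says the trial database holds "all patient reported measures from baseline, 6-month, 18-month, and 33-month surveys".

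On missing data, SAP 7.2 says "We will employ multiple imputations or other suitable techniques deemed appropriate for MAR", without naming the variables in the imputation model.

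The parent plan's 10.1 adjusts the primary analysis for the stratification variables only, and allows other covariates in a sensitivity analysis if they are imbalanced. Its 10.5 assigns self-efficacy and concerns, dichotomised, to logistic regression.

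**The concern.** The power argument in 7.3 applies at least as well to the baseline value of the score under analysis, and 7.3 does not say why the list stops at three variables. Successful randomisation removes the need to adjust for bias. It is no reason to give up precision.

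Beliefs and self-efficacy are the outcomes named in SAP Objective 4.1, even though needs-concerns was only a tertiary outcome in the parent plan (4.5). The SAP introduction reports modest effects on adherence, and the rationale looks for the mechanism behind them. If effects on these intermediate measures are also small, the width of the confidence interval decides whether a null result is informative. Baseline scores that will be tabulated by arm but not modelled leave some of that precision unused.

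**Working it through.** **1. The plan's own figure.** The documents give no sample size, power or precision for BMQ or MASES. The one stated figure, 4714, is for the clinical event rate (parent plan 4.8). It reproduces with two-sided alpha 0.05, 80% power, rate 0.14 per year, 3 years and rate ratio 0.88:

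N = (1.960 × √4 + 0.8416 × √(2 + 2/0.88))² / (3 × 0.14 × (ln 0.88)²) = 4666.97, rounded up to 4667; × 1.01 = 4713.67, rounded up to 4714.

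This figure does not depend on the covariate choice examined here.

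**2. Inputs.** From the documents: N = 4761 (SAP 2), 1:1 allocation, a binary outcome and a log-link model. Assumed: correlation r between baseline and follow-up score of 0.3, 0.5 or 0.7 (taken as given age, sex and income); 20%, 50% or 80% of controls above the cut-off; a shift of 0.1 SD. Data were generated as y = r·x + √(1 − r²)·e + 0.1·arm and y was then dichotomised. The measure is the percentage fall in the variance of the log risk ratio when baseline x is added.

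**3. Full response, robust Poisson, x in fifths** (2,500 replicates):

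| Baseline shape | Above cut-off | r = 0.3 | r = 0.5 | r = 0.7 |
|---|---|---|---|---|
| Normal or lognormal | 50% | 4.9 | 13.5 | 31.8 |
| | 20% | 4.1 | 13.0 | 27.5 |
| | 80% | 3.5 | 11.3 | 24.7 |
| About 30% at the top score | 50% | 4.1 | 13.1 | 30.2 |
| | 20% | 3.4 | 9.6 | 19.2 |
| | 80% | 3.7 | 10.1 | 23.5 |

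A separate run with a normal score (1,000 replicates) gave 4-7%, 12-16% and 24-34%, with no shift in the estimate. Together the ranges are about 3-7%, 10-16% and 19-34%.

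**4. Missing outcomes.** Parent plan 10.3 expects considerable missingness in self-reported outcomes, so this is the more relevant setting. With 60% of outcomes observed at random (an assumption) and x already in the imputation model, adding a linear normal x to the analysis model gave:

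- 20 imputations, 1,500 replicates: 2.9/13.0/16.7 (50% above cut-off), 3.3/7.9/14.6 (20%), 3.7/4.7/13.6 (80%);
- 10 imputations, 1,200 replicates: 1.5/6.4/12.5 (50%), 1.7/5.9/12.7 (20%).

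The range is about 2-4%, 5-13% and 12-17%. Monte Carlo error is up to 2.6 points. Fifths, and missing baseline scores, were not tested in this setting.

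**5. What this means for the interval.** The SE falls by 1 − √(1 − v), where v is the variance reduction. With missing outcomes that is 1-2%, 2.5-7% or 6-9%. With full response and fifths it is 1.5-4%, 5-8% or 10-19%.

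Power example, full response, 50% v 53.98%: log risk ratio 0.0766, SE = √(0.5/(2380.5 × 0.5) + 0.4602/(2380.5 × 0.5398)) = 0.0279, power Φ(0.0766/0.0279 − 1.96) = 78%. With v = 4.9%, 13.5% or 31.8%, power is 80%, 84% or 91%. This is the favourable case.

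**6. The form of the term matters.** Log-binomial regression with a linear normal baseline failed in 22 to 60 of 60 simulated datasets per setting; without the term none failed. With fifths it failed in 0 of 60 in eight settings and 6 of 60 in the ninth. These fits were run in Python, not Stata. A lognormal baseline entered linearly in a Poisson model gained only 2-4% at r = 0.3 and 2-7% at 0.5. At 0.7 it ranged from an 11% gain to a 29% loss.

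**The case against.** Adjusting for stratification variables only is a stated, reasoned choice in both plans, and staying with it keeps this analysis in line with its parent. The correlation is not in the documents. At 0.3 the gain is small: in the power example, 78% becomes 80%. SAP 5.4 lists 18- and 36-month data without saying which follow-up is the endpoint, so the correlation does not even have a defined target. Most of this stands, and it is why the point is an improvement and not a fault. Consistency is the weaker part: parent 10.1 sets its rule for the primary analysis, an event rate with no baseline score to adjust for, and SAP 7.5 already replaces the parent's logistic model.

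A reader might infer that the missing baseline term biases the treatment comparison. It does not. The arms are randomised, and adding the linear normal term moved the mean log risk ratio by at most 0.0006.

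A reader might also infer that the parent plan keeps the baseline scores out of its missing-data models because 10.3 names baseline adherence and not BMQ or MASES. That list is illustrative. The same section plans to use measurements from previous visits to predict loss to follow-up and to include such predictors. SAP 7.2 merely fails to repeat this.

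Finally, a reader might suppose that any baseline term helps, for instance the continuous score in the planned log-binomial model. Step 6 shows that it often would not fit, and that a skewed score entered linearly can lose precision.

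**Conclusion.** The point holds as a cheap improvement. No stated model contains the baseline BMQ or MASES score. Those scores appear to be held, although baseline MASES is inferred from SAP 7.1 and parent section 8; no passage names it.

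The loss is one of precision only. At assumed correlations of 0.3, 0.5 and 0.7, the recoverable variance is about 2-4%, 5-13% and 12-17% with 40% of outcomes missing, and 3-7%, 10-16% and 19-34% with full response and a categorical term. Both sets rest on simulated scores, and the first on a linear normal term. The direction was the same in every setting with fifths or with a normal score. The size cannot be fixed from the documents.

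**What to change.** Make these changes before any comparison of arms:

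1. **SAP 7.3 and 7.5.** State that the models for overall BMQ, BMQ needs, BMQ concerns and MASES adjust for age, sex, income status and the baseline value of the same score. Enter that value in fifths of the baseline distribution pooled over arms, keeping tied values in one category and merging empty categories. This needs no judgement about skewness.
2. **SAP 7.5.** Name robust Poisson regression, already used there for adherence, as the model for these outcomes, so that no switch depends on whether a fit converges.
3. **SAP 7.2.** State that the baseline score enters the imputation model and that missing baseline scores are imputed. This makes explicit what parent 10.3 largely anticipates.

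The cost is wording; no new data are needed. The downsides are three. The named model changes from log-binomial to robust Poisson, though the estimate is still a risk ratio. Some baseline scores will need imputing. And the departure from parent 10.1 and 10.5, made after the parent results were known, must be declared.

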### 7.4. Subgroup analyses

We have specified the subgroups below to conduct analyses with stratifications. We will calculate the effect and confidence interval for each subset. We included subgroup analysis because there may be a subgroup that would benefit more from these interventions.

- a. Age: >70 years vs 65-69 years
- b. Income group: <30,000 vs >30,000
- c. Financial barriers: Present vs Absent
- d. Condition type: Diabetes // CKD // ASCVD // Risk factors only
- e. Multimorbidity: 1-2 vs 3-4 indicated conditions
- f. Primary Care Relational Continuity: Low/Medium vs High
- g. Specialist Involvement in the Year Before Randomization: Yes vs No
- h. On statin at baseline: Yes vs No
- i. On ACE/ARB at baseline: Yes vs No
- j. Living environment: supported living vs. Independent living
- k. Urban / rural

### 7.5. Outcome analysis

#### Tests for Objective #1:

We will conduct log-binomial regression to estimate the effect of the two interventions on belief about medication and medication self-efficacy and needs concern. Similarly, medication adherence will be analyzed using Robust Poisson Regression.

#### Tests for Objective #2:

We will conduct Factorial ANOVA with or without a posthoc test to assess how medication adherence changes over time.

All analyses will be conducted using the intention to treat principle.

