## 3. Rationale

Medication non-adherence leads to poor health outcomes (12). One of the pillars of chronic disease management is improving self-efficacy, a capacity to perform behaviors desirable to improved health (13). Higher self-efficacy positively correlates with improved outcomes and reduced healthcare utilization (14).

Cost-related non-adherence in Canada is much higher than in other countries comparable to Canada (15). Copayments and deductibles associated with medications are some of the main reasons why people do not take their medication as prescribed (16).

With the exception of our findings from the ACCESS trial, there is a paucity of evidence on how interventions, including removing financial barriers, might lead to better adherence to medication among people with chronic illnesses in a Canadian context. Even after our initial study was published question remain regarding the mechanism of action of the changes observed. We seek to understand further how the interventions impacted adherence to statins and ACEi/ARBs by assessing and comparing adherence at specific periods after the interventions and how the interventions may have impacted several patient-reported measures related to medication adherence.

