##### **4.2. To understand the dynamic changes in medication adherence through time by assessing whether there is a significant difference in adherence at different points during the study period.**

#### **5. Methodology**

##### **5.1. Trial Design**

The trial was designed as a researcher-blinded, parallel, factorial 2x2 pragmatic randomized control trial. Participant blinding was not possible due to the nature of the interventions. The data from the trial will be used to analyze subjects of interest for this secondary outcome analysis paper.

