**c. Medication Adherence (PDC)**

Adherence to the high-value cardiovascular medications, including Angiotensin Convertase Enzyme (ACE) inhibitors, Angiotensin Receptor Blockers (ARBs), and statins, will be assessed by calculating the proportion of days covered (calculated using the formula below) (sum of days covered in the period of interest (POI))  $\div$  (number of days in the POI)  $\times$  100% (18). Those with 80% or greater PDC are considered adherent, and vice versa.

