4.6. Timing of outcomes as assessments

The primary outcome data was ascertained through administrative health data held within the province of Alberta, including linked datasets such as: laboratory data, pharmacy dispensation data, acute care data, outpatient physician claims data, and demographic data. Participants were followed for a minimum of 2.5 years from the time of randomization through until March 30, 2021. This data will be available as of early 2022.

Self-reported outcome measures were obtained via electronic and paper-based surveys which were sent to participants 6-, 18-, and 33-months after randomization.

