6.2. Definition of Medication Adherence

Data extracted from the Pharmacy Information Network will be used to calculate the Proportion of Days Covered (PDC): “number of days dispensed”/“number of days between prescription renewals” (42,43) using drug data in the ICDC Chronic Disease Repository. Patients with medication supplies to cover $\geq 80\%$ of observed treatment days are considered adherent (44,45).

We will calculate PDC for each participant in the initial 12-month period that they were in the trial for both Statins and ACEi/ARBs. For those switching between statins or agents within the ACE/ARB class, ANY dispensed medication in the class will be included in the analysis.

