10.5. Analysis Methods- Secondary Outcomes

Medication adherence is a binary variable and will be analyzed using log binomial regression (generalized linear models with a log link)—given the likely high prevalence of non-adherence.

EQ5D index scores are continuous and will be analyzed using linear regression.

Medication self-efficacy and concerns will be dichotomized and analyzed using logistic regression.

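### Objective 2 compares adherence between periods in the same participants, but the SAP names only a factorial ANOVA, with no within-person term, outcome form or PDC windows

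*SAP*

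**What the plan says.** SAP section 4.2 sets the objective: "To understand the dynamic changes in medication adherence through time by assessing whether there is a significant difference in adherence at different points". The Rationale (SAP section 3) describes it as "assessing and comparing adherence at specific periods after the interventions". The only method given, in SAP section 7.5 under the tests for Objective 2, is "We will conduct Factorial ANOVA with or without a posthoc test to assess how medication adherence changes over time".

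On the outcome, SAP section 5.3c defines PDC as a percentage of days and then adds a cut-off: "Those with 80% or greater PDC are considered adherent, and vice versa". Section 7.5 does not say which form enters the ANOVA. On timing, SAP section 5.4 lists baseline, 18 months and 36 months. These are time points, whereas PDC needs a window of days.

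The combined protocol and SAP (the parent plan) does not fill these gaps:

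- **Window:** section 6.2 defines one, with "We will calculate PDC for each participant in the initial 12-month period that they were in the trial for both Statins and ACEi/ARBs".
- **Outcome and model:** section 10.5 states "Medication adherence is a binary variable and will be analyzed using log binomial regression".
- **Follow-up:** section 4.6 states "Participants were followed for a minimum of 2.5 years from the time of randomization".
- **Longitudinal model:** section 6.3 plans mixed models over time, but only for EQ-5D.

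**The concern.** Repeated adherence values from one person are correlated. An ordinary factorial ANOVA treats every person-period row as independent, so stable differences between people stay in the error term. Comparisons of periods, and of change between arms, then look less precise than they are. Arm effects averaged over periods go wrong in the opposite direction, because the same people are counted more than once.

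The sentence in section 7.5 allows three readings:

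1. An ordinary factorial ANOVA on person-period rows, with the errors just described.
2. A repeated-measures or mixed ANOVA, for which the standard-error problem largely disappears.
3. A separate 2x2 ANOVA in each period, in which change over time is not tested at all.

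At stake is whether small real changes in adherence can be seen. The SAP's Introduction calls the adherence effects already found in this trial modest, and the Rationale is to understand how they arose, so small changes are relevant. The undefined windows add a different risk: the share of people at or above 80% PDC depends on window length, so unequal windows can show a change when use has not changed.

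**Working it through.** **The plan's own figure.** Neither document gives a power or precision figure for Objective 2. The only design figure is the trial sample size for the primary event rate (combined protocol and SAP, section 4.8). It reproduces with the Poisson-regression formula: (1.96·√4 + 0.84·√(2 + 2/0.88))² / (3 × 0.14 × ln(0.88)²) = 4667, and 4667 × 1.01 = 4714. It says nothing about power for change in adherence.

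**Inputs from the documents.** Participants N = 4761 (SAP section 2); significance level 0.05 (SAP section 6.1), taken as two-sided; 1:1 allocation (parent plan section 4.8).

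**Assumptions, not in the documents.** Within-person correlation ρ = 0.3, 0.5 or 0.7, equal between all periods; two periods unless stated; everyone contributes to both. For binary PDC, 70% adherent, so SD = √(0.7 × 0.3) = 45.8 points. For percentage PDC, SD = 25 points.

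**Step 1: standard error of a change.** The true value is SD·√(2(1−ρ)/N). The ordinary ANOVA uses SD·√(2/N). The ratio is 1/√(1−ρ) = 1.20, 1.41, 1.83.

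**Step 2: true size of the nominal 5% period test.** With three periods it is P(χ² on 2 df > 5.99/(1−ρ)) = 1.4%, 0.25%, 0.005%. The test is conservative.

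**Step 3: overall change detectable with 80% power.**

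- Within-person analysis: (1.96 + 0.84)·SD·√(2(1−ρ)/N)
- Ordinary ANOVA: 1.96·SD·√(2/N) + 0.84·SD·√(2(1−ρ)/N)

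| N = 4761 | ρ = 0.3 | ρ = 0.5 | ρ = 0.7 |
|---|---|---|---|
| Binary PDC, within-person | 2.2 | 1.9 | 1.4 |
| Binary PDC, ordinary ANOVA | 2.5 | 2.4 | 2.3 |
| Percentage PDC, within-person | 1.2 | 1.0 | 0.8 |
| Percentage PDC, ordinary ANOVA | 1.4 | 1.3 | 1.2 |

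Example, binary PDC at ρ = 0.5: SD·√(2/N) = 0.94 and SD·√(2(1−ρ)/N) = 0.66. This gives 2.80 × 0.66 = 1.9 against 1.96 × 0.94 + 0.84 × 0.66 = 2.4 points. An arm-by-period difference has twice the standard error, so every entry doubles.

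**Step 4: fewer contributors.** The number of participants with a PDC for each drug class is not given, so half of 4761 (N = 2380) is used as an illustration. Power for a 5-point arm-by-period difference is:

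| N = 2380 | ρ = 0.3 | ρ = 0.5 | ρ = 0.7 |
|---|---|---|---|
| Binary PDC, within-person | 61% | 76% | 93% |
| Binary PDC, ordinary ANOVA | 46% | 46% | 44% |
| Percentage PDC, within-person | 98% | 99.8% | 100% |
| Percentage PDC, ordinary ANOVA | 96% | 98% | 99.7% |

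A 5-point overall change is detected with at least 98% power by the ordinary ANOVA even with 2380 people and binary PDC.

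**Step 5: arm effects averaged over two periods.** In the ordinary ANOVA the type I error is 2·(1 − Φ(1.96/√(1+ρ))) = 8.6%, 11.0%, 13.3%.

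**Step 6: window length.** Stable on/off medication use was simulated for 20,000 people, with assumed mean spells of 200 to 400 days on and 30 to 90 days off. The share with PDC of 80% or more in 6-month windows ranged from about 3 points below to 8 points above the share in 12-month windows, while mean PDC stayed essentially the same. Across five equal 6-month windows the share varied by only about 1 point, which is simulation noise.

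**The case against.** The strongest reply is that nothing in the SAP says the ANOVA will ignore the repeated structure. A factorial ANOVA can carry a within-person factor, and an analyst may well have meant that. This stands: what the documents show is an incomplete specification, and the loss of precision is conditional on the ordinary form being run.

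A second reply is that ANOVA is ordinarily used for a continuous outcome and section 5.3c defines PDC as a percentage. Binary PDC for Objective 1 and percentage PDC for Objective 2 is then a coherent plan, and with percentage PDC the power loss is slight. This also stands. The marked loss in step 4 needs both binary PDC and about half the participants. The parent plan's statement that half are not receiving statins concerns Albertans with these chronic diseases; it is not a count of trial participants with a PDC.

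Third, section 7.5 asks how adherence changes over time and does not state an arm-by-period contrast, where the loss is largest. That contrast can be inferred from the factorial design and the Rationale, but the SAP does not write it down. The documents also give no minimal important difference for adherence.

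A reader might go further and infer that the ANOVA will produce false findings of change. For the period tests themselves the error is in the other direction. Only unequal windows could create an apparent change, and the SAP does not say that windows will be unequal. A reader might also infer that the arm comparisons on adherence are invalid. SAP section 7.5 assigns those to robust Poisson regression under Objective 1, so the inflated error in step 5 matters only if arm effects are read from this ANOVA.

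**Conclusion.** The gap is real and worth closing, and its consequence is moderate. Objective 2 rests on a within-person comparison, and its one-sentence method leaves open the error structure, the form of the outcome and the windows.

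If an ordinary ANOVA is run, tests of change are conservative. At correlation 0.5 with everyone contributing, the detectable overall change rises by about 0.5 point for binary PDC or 0.3 point for percentage PDC. The loss is larger for differences in change between arms or with fewer contributors. Large changes are found either way, and under a repeated-measures ANOVA the loss largely disappears. These sizes rest on the assumed correlation, adherence level, SD and two complete periods.

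The outcome form and the windows need settling under every reading. The parent plan defines only the first 12 months, and a 36-month endpoint is not guaranteed for people followed for the 2.5-year minimum. It does not follow that few people reach 36 months: section 4.8 of the parent plan assumed an average follow-up of 3 years.

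**What to change.** In SAP section 7.5, replace the factorial ANOVA with an analysis that accounts for repeated values per participant. It should include period, both interventions, intervention-by-period terms, and the covariates of SAP section 7.3 (age, sex, income status).

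- **If PDC of 80% or more is the outcome:** use the robust Poisson model already planned for adherence, with variance clustered on participant.
- **If PDC as a percentage is the outcome:** use a linear mixed model or a repeated-measures ANOVA. If the latter was intended all along, saying so is enough for this part.
- **Outcome form:** state which is primary. The Poisson model tests differences in change as ratios and the linear model as percentage points, and the two can disagree.
- **Windows:** define PDC windows of equal length that fit within the 2.5-year minimum follow-up, for example two of 12 months or five of 6 months. Give any pre-randomisation window the same length. Say how the windows relate to the 18- and 36-month points in SAP section 5.4.
- **Tests:** state a joint test of the period effects for overall change, and a joint test of the intervention-by-period terms for each intervention.

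The cost is SAP wording, a window definition, a different Stata command and slightly more analysis work. The pharmacy data are already planned for. The downside is that many windows mean joint tests with more degrees of freedom (4 for five windows), which have less power against some patterns of change.

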4.13. Trial Comparisons

The impact of the two interventions will be conducted independently of one another. We will compare each intervention arm to those who did not receive that specific intervention.

5. Statistical Principles

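### Objective 2 is worded as change in adherence over time and names no intervention-by-period test, although the rationale asks how the interventions affected adherence in specific periods

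*SAP*

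**What the plan says.** The SAP rationale (section 3) gives the purpose: "We seek to understand further how the interventions impacted adherence to statins and ACEi/ARBs by assessing and comparing adherence at specific periods after the interventions".

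Objective 4.2 turns this into "assessing whether there is a significant difference in adherence at different points during the study period". The analysis line in section 7.5 is: "We will conduct Factorial ANOVA with or without a posthoc test to assess how medication adherence changes over time". It does not list the factors or say which effect is the test. The PDC periods are not defined for this objective. The SAP also does not say whether PDC is analysed as a percentage or as adherent/non-adherent at 80%.

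Section 6.1 sets the reporting rule: "We will consider findings as significant for P-values of 0.05 or lower".

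Adherence appears once more, under the Objective 1 tests: "Similarly, medication adherence will be analyzed using Robust Poisson Regression". No period or time term is given there.

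**The concern.** The rationale poses a between-arm question asked period by period. The natural reading of Objective 4.2 and its test is a within-cohort question: does average adherence differ between time points? A test of that hypothesis makes no use of the randomized comparison. Making it a correct repeated-measures test would not change this.

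Adherence to long-term drugs may drift over three years whatever the allocation. In a paper about two interventions, a significant time effect could then be read as saying something about them when it does not. In the other direction, if arms diverge, averaging over them shrinks the time effect and can hide part of the divergence.

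**Working it through.** **1. Does another section supply the missing contrast?**

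- SAP 7.5, Objective 1: the robust Poisson model is between-arm by implication, but no period is attached to it.
- Combined protocol and SAP, 4.13: "We will compare each intervention arm to those who did not receive that specific intervention". This is a between-arm rule with no time element.
- Combined protocol and SAP, 6.2: PDC is calculated for the first 12 months only, so there is one period.
- Combined protocol and SAP, section 11: the interaction considered is between the two interventions, not with time.
- Combined protocol and SAP, 6.3: EQ-5D scores are compared between groups over time with mixed models. That is the structure Objective 2 lacks, but it is not specified for adherence.

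So no intervention-by-period contrast for adherence is stated anywhere.

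**2. If the ANOVA has three factors.** Copayment, education and time give 2³ − 1 = 7 effects: three main effects, three two-way interactions and one three-way interaction. The only one the text describes is time.

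**3. Illustration of the consequence.** The plan gives no power figure for Objective 2. The 4714 in SAP 5.6 is for the parent trial's primary outcome (4667 × 1.01 = 4713.7) and does not bear on this point.

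From the documents: N=4761 (SAP introduction) and alpha 0.05 (SAP 6.1). Assumed: three equally spaced periods, two equal arms, 70% adherent at the start, latent within-person correlation 0.6, no missing data. N=2000 is a second assumed value, because not everyone will contribute PDC for a given drug class.

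For a linear change of s per period, the 2-df test has noncentrality

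λ = (N/m) × 2s² / [p(1−p)(1−ρ)].

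Here m=1 for the time effect, with s the average change over arms. For arm-by-period m=4, with s the between-arm difference in change. A latent correlation of 0.6 at about 70% adherence gives a covariance of 0.0845 between yes/no values, so ρ = 0.0845/√(0.21 × 0.2176) = 0.395. With p=0.68 (the middle period), the denominator is 0.2176 × 0.605 = 0.1316. Power is the chance that a noncentral chi-square on 2 df exceeds 5.99.

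- *Both arms fall 2 points per period, no intervention effect.* Time: λ = 4761 × 0.0008/0.1316 = 28.9, power 99.9%. At N=2000, λ = 12.2, power 89%. Simulation gave 99.8% and about 87%. Arm-by-period: λ = 0, so 5% (3% to 6% in simulation).
- *Both arms fall 1 point per period.* Time: λ = 4761 × 0.0002/0.1316 = 7.2, power 67% (simulation 67%). Arm-by-period: 5%.
- *Controls fall 2 points, intervention arm flat.* The average change is again −1, so the time test has the same 67% and cannot tell this case from the previous one. Arm-by-period: λ = (4761/4) × 0.0008/0.1316 = 7.2, power 67%.
- *Controls fall 2 points, intervention arm rises 1.* The average change is −0.5. Time: λ = 4761 × 0.00005/0.1316 = 1.8, power 21%. Arm-by-period (difference 3): λ = (4761/4) × 0.0018/0.1316 = 16.3, power 96%.

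On continuous PDC (assumed SD 20 to 30 points, correlation 0.3 to 0.6), a common change of 2 points in total from first to last period makes the time test significant in 95% to 100% of trials at N=4761, and in 61% to 99.6% at N=2000.

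**The case against.** The strongest reply is that the text is open rather than wrong. A factorial ANOVA needs at least two factors, and in a 2x2 trial the obvious ones besides time are the interventions. Objective 4.2 speaks of a difference at different points, which could mean a group difference assessed at each point, and the rationale favours that reading. Intention to treat is applied to all analyses, which has little meaning without randomized groups. Nowhere does the SAP say that arms are pooled. The robust Poisson model could also be run by period.

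Much of this stands. A reader might infer that the SAP has settled on a pooled time test and that Objective 2 cannot answer the rationale's question. The documents do not establish that. Nor is a significant time effect a false positive for Objective 4.2 read literally. It misleads only if presented as an intervention effect, and the SAP does not say it will be.

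A reader might also infer that opposite trends would cancel to nothing. That needs arms of equal size with equal and opposite trends. With changes of 2 points per period each way from 70%, the arms would stand at 66% and 74% by the third period, an 8-point gap. This sits poorly with the modest adherence gains reported in the SAP introduction. Partial masking is the more realistic risk.

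The reply does not remove the gap. On the generous reading, the effect that answers Objective 2 is still unnamed, and the follow-up contrasts remain optional because the test line allows the analysis with or without them.

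**Conclusion.** The point holds as a mismatch between question and stated test, together with an unspecified model. It does not show that the wrong analysis will certainly be run. It is more than missing detail, because the only hypothesis worded for Objective 2 makes no use of the randomized comparison.

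The percentages are conditional on taking the time effect as the Objective 2 result and on assumed drift, adherence level, correlation and number of contributors. The direction does not depend on those values: a time effect averaged over arms contains no between-arm contrast. As this is a secondary analysis, the change should be made but does not threaten the parent trial's results.

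**What to change.** - Align Objective 4.2 with the rationale: ask whether the effect of each intervention on adherence differs between periods.
- In 7.5, list the ANOVA factors, define the PDC periods and state the outcome scale.
- Name copayment-by-period and education-by-period as the Objective 2 tests, in a model that allows for repeated measures on the same person. Treating the repeated values as independent would distort the test: in simulation with no time effect, such an ANOVA rejected in only 1.5% (correlation 0.3) or 0.05% (correlation 0.6) of trials instead of 5%.
- Report as fixed output the between-arm adherence difference with 95% CI in each period, for each intervention, separately for statins and ACEi/ARBs. This is needed as well as the interaction, since an effect that is constant across post-randomization periods would not appear in the interaction.
- The overall time trend may still be reported, but not as evidence of an intervention effect.

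The cost is SAP wording, with the same pharmacy data. The downside is precision: for a change of the same size, the interaction has a quarter of the noncentrality of the overall time effect (m=4 against m=1), so fewer results will reach significance.
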